3.5 Data handling conventions

In general, data from the source documents will be captured in an eCRF by a software package that can be customized for remote data entry procedure and that maintains an electronic audit trail. The eCRFs will be developed in the EDC system in accordance with bioskin SOPs under supervision and in agreement with the sponsor. The database structure will be validated.

Only authorized site personnel will be able to enter/modify/correct data to the eCRF. The investigator/coordinator or designee must enter the information required by the protocol as soon as possible after the visit into the eCRF.

The data will be checked for consistency. Queries for discrepant data may be generated automatically by the system upon entry or generated manually by the monitor or the trial data manager. All queries, whether generated by the system or by a user, will be in an electronic format. Once all the queries are closed and data have been verified by the CRA, the eCRF will be signed (eSignature) by the investigator and the database will be locked.

All data management procedures will be detailed in a separate, specifically identified file that collectively will be referenced as the data management plan (DMP).

Adverse event, medical history terms, and procedures from the concomitant medications page will be coded using the MedDRA dictionary (Version 20.1 from September 2017) according to the ICH MedDRA Term Selection: Points to Consider release 4.14 from September 2017. All MedDRA coded terms will be provided with all 5 levels, from System Organ Class to Lowest level term, including associated codes.

Previous and concomitant medication and non-drug therapies will be coded using the WHO Drug Global Dictionary in its latest available version at the time point of coding. Product Name, Preferred Base Name, Drug Code and ATC Levels 1-4 with associated codes will be reported.

The locked SAS Database will be used to generate the subject listings, tabulations, and analyses.

All data associated with the clinical database, including eCRF data, all external data such as medical coding, third party data, and others i.e. randomization unblinding, analysis population definition, all transferred to study data tabulation model (CDISC SDTM, v1.4; IG v3.2). The SDTM data sets will be used to generate analysis data model (CDISC ADaM, v2.1; IG v1.1) data sets, subject listings, tabulations, and analyses.

3.5.1 Missing data

A description of missing data will be provided in the clinical study report.

For the evaluation of success rates of the primary efficacy variables PASI and PGA missing PGA assessments and/or any parts of the PASI assessments will be evaluated as failure to achieve improvement.

For descriptive analyses of PASI, PGA and BSA the last observation carried forward (LOCF) principle will be applied to impute the missing assessments, up to the Day 84 visit. Follow-up assessments will not be imputed.

Sensitivity of the primary efficacy analyses will be evaluated applying PP analyses.

Regarding incomplete recordings for adverse events the following rules apply:

- For start and stop dates no imputation will be applied. If any, start or stop date, is not complete, but required for the classification, i.e. the occurrence of the AE is not explicitly reported as occurring prior first dose (see eCRF), the AE will be considered treatment emergent.
- Missing assessments of severity, intensity and causal relationship to the IMP will be reported as a separate category.

For the determination of the number of years from start of psoriasis to the screening visit missing starting days will be imputed by the first day of month and missing months will be imputed by the first month (January) of the year.

For concomitant therapies (see section 3.2.2.4) incomplete dates will not be imputed. If an incomplete start or stop date does not allow for the classification as prior and/or concomitant therapy - despite of information in eCRF if taken/used prior to first dosing and/or if ongoing at first dosing - the treatment will be reported as prior and as concomitant therapy.

Pharmacokinetic data below LLQ will be replaced as described in 3.4.7.3 for descriptive statistics and for the derivation of $AUC_{(0,t)}$. Missing pre-dose levels will be imputed by zero. Missing intermediate samples, i.e. missing values in between non-missing levels (quantifiable or substituted by LLQ/2) will be imputed by linear interpolation between the last preceding and the next following available value. The last value will be imputed by LLQ/2, if missing.

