3.3 Analysis populations

3.3.1 Efficacy populations

Intent-To-Treat (ITT)

The full-analysis-set (FAS) will include all randomized patient who received at least one dose of IMP, and had at least one post-baseline assessment. The intention-to-treat (ITT) analysis will be based on the FAS. The FAS is considered primary analysis set for the efficacy analysis.

Per-Protocol (PP)

The valid-cases-set (VCS) will include all patients from the FAS, who completed the assessments of the co-primary endpoints without any protocol violation interfering with the precise evaluation of treatment efficacy and with sufficient exposure to IMP, i.e.

- who completed the visit 5 (Day 84) assessments of PASI and PGA;
- who did not take any prohibited concomitant medications up to the visit 5 (Day 84).

During the blind data review meeting (BDRM) concomitant medications will be reviewed considering timing, duration of concomitant treatment, and influence on the efficacy assessments to determine prohibited medication usage that warrants exclusion from the VCS;

- who were compliant with the dosing regimen. A subject will be considered compliant, if the subject administered $\geq 80\%$ of the planned capsules.

Subjects who prematurely discontinue the treatment due to an adverse event at least possibly related to IMP will not be excluded from the VCS.

Prior to breaking the blind, other additional criteria may be added to the list to accommodate for unforeseen events that occurred during the conduct of the trial that result in noteworthy study protocol violations.

The per-protocol (PP) analysis will be based on the VCS. Primary efficacy endpoints will be evaluated on VCS to assess the sensitivity.

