3.5.3 Unscheduled visits

If applicable, the reason for unscheduled visit assessments will be given together with the results. For the statistical analysis the unscheduled assessments will be assigned as described in section 3.5.2.

In case of premature withdrawal from the trial, efficacy assessments performed at the time point of withdrawal, will be assigned to a planned visit as described in section 3.5.2.

Safety assessments performed at the time point of withdrawal will be reported together with the last visit in treatment phase (Day 84 / End of Treatment [EoT]).

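### No planned analysis isolates the missing = failure rule: the only declared sensitivity analysis of the co-primary endpoints is per protocol, which mixes missing Day 84 scores with other exclusions

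*SAP*

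**What the plan says.** - **Primary rule.** For the success rates, "missing PGA assessments and/or any parts of the PASI assessments will be evaluated as failure to achieve improvement" (SAP 3.5.1; protocol 6.6 has the same rule).
- **Primary set.** The FAS takes randomized patients "who received at least one dose of IMP, and had at least one post-baseline assessment" (SAP 3.3.1).
- **Sensitivity.** SAP 3.5.1 and protocol 6.6: "Sensitivity of the primary efficacy analyses will be evaluated applying PP analyses". SAP 3.3.1 repeats it: "Primary efficacy endpoints will be evaluated on VCS to assess the sensitivity".
- **Who is in the VCS.** FAS patients "who completed the visit 5 (Day 84) assessments of PASI and PGA", with no prohibited medication up to that visit and at least 80% of the planned capsules. There is one exception: "Subjects who prematurely discontinue the treatment due to an adverse event at least possibly related to IMP will not be excluded from the VCS".
- **Withdrawals.** SAP 3.5.3: "efficacy assessments performed at the time point of withdrawal, will be assigned to a planned visit as described in section 3.5.2". Protocol 5.5.1 asks for an Early Termination Visit, where possible, with the Visit 5 procedures.
- **Table shells.** The responder shells (14.3.3 and 14.3.9 for PASI 75, 14.3.15 and 14.3.18 for PGA improvement) are all titled LOCF. SAP 3.5.1 reserves LOCF for the descriptive analyses.

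No multiple imputation, tipping-point or best/worst-case analysis of the responder endpoints in the FAS is declared.

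**The concern.** A sensitivity analysis for a missing-data rule should hold the population fixed and change what is assumed about the unobserved outcomes. The per-protocol analysis does the reverse. It removes most of the patients to whom the rule applies, and it removes others for reasons that have nothing to do with missing data. If FAS and VCS differ, the reader cannot tell which change caused it. If they agree, two effects may have cancelled.

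Missing = failure is often taken to be conservative. It is so only when the active arm loses at least a comparable share of its responders. If placebo loses more patients, the rule removes more would-be responders from placebo and widens the difference; if the active arm loses more, it narrows it. At stake is whether the report can say how far a co-primary result depends on the rule. The LOCF titles add a more basic doubt about which rule will produce that result.

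**Working it through.** **1. The plan's own figure.** SAP 2.2: rates 0.674 and 0.40, two-sided α 0.10, power 80%, 40 per group, about 150 recruited for 120 evaluable. With mean rate 0.537:

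n = [1.645·√(2·0.537·0.463) + 0.842·√(0.674·0.326 + 0.40·0.60)]² / 0.274² = 39.9, so 40 per group (power 0.801).

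120 / (1 − 0.20) = 150, or 50 per arm. The figure reproduces.

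**2. Assumptions for the illustrations.** The documents give no dropout by arm, so all splits below are assumed. There are 50 FAS patients per arm. Observed patients respond at 0.674 (active) or 0.40 (placebo), with counts rounded. P-values are from the uncorrected, unstratified χ² test, as an approximation to the planned stratified CMH test.

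**3. Three splits around 20% missing.** Observed responders are:
- 10/10 missing: 0.674·40 ≈ 27; 0.40·40 = 16.
- 5/15 missing: 0.674·45 ≈ 30; 0.40·35 = 14.
- 15/5 missing: 0.674·35 ≈ 24; 0.40·45 = 18.

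| Missing, active/placebo | Missing = failure | Completers only |
|---|---|---|
| 10/10 | 27/50 v 16/50: 0.22, p 0.026 | 27/40 v 16/40: 0.275, p 0.014 |
| 5/15 | 30/50 v 14/50: 0.32, p 0.001 | 30/45 v 14/35: 0.267, p 0.017 |
| 15/5 | 24/50 v 18/50: 0.12, p 0.22 | 24/35 v 18/45: 0.286, p 0.011 |

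If missing patients respond at 40% in both arms:
- 5/15: (30+2)/50 v (14+6)/50 = 32/50 v 20/50, difference 0.24, p 0.016.
- 15/5: (24+6)/50 v (18+2)/50 = 30/50 v 20/50, difference 0.20, p 0.046.

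Against that reference, missing = failure overstates the difference by 0.08 in the 5/15 split and understates it by 0.08 in the 15/5 split. The completer figure moves in the right direction but does not land on the reference, and the real VCS would also carry its other exclusions.

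**4. No true effect.** Assume 40% response in both arms and dropout unrelated to outcome. The observed rate under the rule is 0.40·(1 − dropout).
- 20%/20%: 0.32 v 0.32, difference 0.
- 10%/30%: 0.36 v 0.28, difference 0.08. The chance of a result favouring the drug at two-sided 0.10 is 22.4%, against a nominal 5%. Completers (45 v 35) give 5.2%.
- 30%/10%: difference −0.08, against the drug.
- 10%/30% at a 10% response rate: 0.09 v 0.07, difference 0.02, chance 10.9%.

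**5. What a tipping point would add.** Assume 5 active and 15 placebo missing, and completers 24/45 v 14/35. Missing = failure gives 24/50 v 14/50, difference 0.20, p 0.039. With active missing patients kept as failures, 2 responders among the 15 missing placebo patients give 24/50 v 16/50, p 0.102, and 10 give a difference of 0. In the stronger 5/15 case of step 3, it takes 8 of 15 (30/50 v 22/50, p 0.109). Neither planned analysis would separate a fragile result from a sturdier one in this way.

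**The case against.** The other side has real points.

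- **The per-protocol analysis is not blind to the problem.** It is close to a complete-case analysis. In the 5/15 example it falls from 0.32 to 0.267, and under the null with 10%/30% dropout it brings the false-positive chance back to about nominal. A reader might infer that it cannot test the rule at all. That does not hold: it reacts when dropout is unrelated to outcome within arm. What stands is that it does not isolate the rule and says nothing about outcome-related dropout.
- **The VCS does not exclude everyone with missing scores.** Patients who stopped for an at least possibly related adverse event stay in, and if their Day 84 scores are missing they count as failures there too.
- **Fewer outcomes may be imputed than 30 of 150.** The documents do not define evaluable as having Day 84 scores. Some withdrawal assessments can be assigned to Day 84, and patients with no post-baseline assessment leave the FAS. The 20% missing used above is therefore an assumption and may be too high.
- **The direction is open.** A reader might infer that the rule favours the drug. Nothing in the documents shows that placebo will lose more patients, and with equal dropout the rule shrinks the difference (0.22 against 0.275).
- **The consequence is limited.** There are no formal hypotheses, p-values are descriptive, and discontinuations before Week 12 are tabulated by arm with reasons, so unequal dropout would be visible.

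All of these stand, and they narrow the point. None supplies an analysis that varies the missing outcomes in the FAS.

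**Conclusion.** The concern holds in a limited form. Per protocol is the only declared sensitivity analysis for the co-primary endpoints. It changes the population for several reasons at once, so a gap between FAS and VCS cannot be ascribed to missing = failure, and dropout related to outcome goes unexamined.

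Under the assumed splits, the rule moves the difference by about 0.08 in either direction relative to a 40% response among missing patients. These sizes rest on 20% missing overall, the SAP's illustrative rates and an unstratified test. Fewer missing patients or lower response rates would make them smaller.

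Separately, the LOCF titles of the responder shells conflict with SAP 3.5.1. If the shells are run as titled, the reported co-primary result would not use missing = failure at all. This is a worthwhile, inexpensive improvement to an exploratory trial, not a flaw that invalidates its analysis.

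**What to change.** In SAP 3.5.1, keep the per-protocol analysis as supportive and add two FAS analyses for each co-primary endpoint and each dose against placebo:

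1. **Tipping-point grid** over the number of missing patients counted as responders in each arm, showing the difference and p-value per cell. State how these responders are spread over the pooled centers, or use an unstratified test for the grid.
2. **Multiple imputation** of Day 84 PASI and PGA by arm from baseline and observed visits, then the responder rule and the CMH analysis, with results combined over imputations.

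Also reconcile the titles of shells 14.3.3, 14.3.9, 14.3.15 and 14.3.18 with the text, so that one rule clearly produces the co-primary result. If LOCF responder rates are wanted as well, give them separate tables labelled as such.

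Cost: one SAP paragraph, extra programming and two tables, with no new data or patients. The downside is more output in an exploratory trial. Protocol section 6 lets changes in statistical methods before database lock be recorded in the SAP without an amendment; SAP 1.3 is the place to note them.

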3.5.2 Window for time points

A strict adherence to the visit schedule will be required. Visit schedule violations will be documented as protocol deviations and assessed within the BDRM.

Assessments performed out of the planned visit schedule will be assigned to the nearest, directly preceding or following planned visit, if that visit is missing. If both planned visits are missing and the distances are equal, the assignment is performed to the following one. Otherwise an assessment performed out of the planned visit schedule will not be included in the statistical evaluation and will be listed only.

3.5.3 Unscheduled visits

If applicable, the reason for unscheduled visit assessments will be given together with the results. For the statistical analysis the unscheduled assessments will be assigned as described in section 3.5.2.

In case of premature withdrawal from the trial, efficacy assessments performed at the time point of withdrawal, will be assigned to a planned visit as described in section 3.5.2.

Safety assessments performed at the time point of withdrawal will be reported together with the last visit in treatment phase (Day 84 / End of Treatment [EoT]).

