- Check concomitant therapy and adverse events
- Record vital signs
- Drug return / accountability and re-dispensation of unused kits/blister
- Diary collected and checked
- *Photographic documentation only for a subgroup (see section 5.5.1.4)*
- Urinalysis (see section 5.5.2)
- Collection of samples for determination of laboratory parameters (hematological status, clinical chemistry, urinalysis, see section 5.5.2)
- PASI (see section 5.5.1.1)

- PGA (see section 5.5.1.2)
- BSA (see section 5.5.1.3)
- Dispensing of IMP and diary

Trial Day 84 (week 12, visit 5) (EoT)

- Check concomitant therapy and adverse events
- Physical examination (see section 5.5.5)
- Record vital signs (see section 5.5.3)
- Urine pregnancy test and urinalysis (see section 5.5.2)
- *Photographic documentation only for a subgroup (see section 5.5.1.4)*
- Collection of samples for determination of laboratory parameters (hematological status, clinical chemistry, see section 5.5.2)
- *PK samples only for a subgroup (see section 5.5.1.5)*
- Last IMP administration at site for all patients
- Drug return / accountability
- Diary collected and checked
- PASI (see section 5.5.1.1)
- PGA (see section 5.5.1.2)
- BSA (see section 5.5.1.3)

Trial Day 112 (week 16, visit 6, Follow-up) (End of Study, EoS)

- *Photographic documentation only for a subgroup (see section 5.5.1.4)*
- Check concomitant therapy and adverse events
- Physical examination (see section 5.5.5)
- Record vital signs (see section 5.5.3)
- Urinalysis(see section 5.5.2)
- Collection of samples for determination of laboratory parameters (hematological status, clinical chemistry, see section 5.5.2)
- PASI (see section 5.5.1.1)
- PGA (see section 5.5.1.2)
- BSA (see section 5.5.1.3)

The patients must be present at site for approximately 60 minutes on Screening and Day 1, 45 minutes on Day 28 and 56, 60 minutes on Day 84 and 45 minutes on Day 112.

The above mentioned time will be extended for 15 minutes for patients with photographic documentation on each visit.

The above mentioned time will be extended on Day 1 and Day 84 for 120 minutes for patients with PK sampling.

Early Termination Visit

Patients who discontinue early from the trial should, if possible, have an Early Termination Visit. This visit should take place as soon as possible after the patient stops taking IMP. The observations and procedures scheduled for Visit 5 (End of Treatment) should be performed at the Early Termination Visit.

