3.1 Definitions

The following definitions apply:

- Baseline: The latest non-missing observation prior to first treatment with IMP.

Baseline data definition	obtained on/at
Age, race, height, body weight, BMI	Screening
Relevant medical history (last 5 years) including psoriasis history, relevant surgical history (last 5 years) and relevant previous medication (last 6 weeks) including psoriatic treatment taken (last 6 weeks)	Screening
Smoking and alcohol consumption	Screening
Concomitant medication	Day 1
Adverse events	Day 1
Physical examination	Day 1, Screening*
Vital signs (blood pressure, pulse rate)	Day 1, Screening*
Safety laboratory parameters	Day 1, Screening*
PASI, PGA, BSA	Day 1, Screening*

*only in case of missing Day 1 assessment

- Change from baseline = post baseline value – baseline value
- Percent change from baseline = $100 * \text{change from baseline} / \text{baseline value}$
- Last observation carried forward (LOCF): The last observed value (either scheduled or unscheduled) carried forward and used for all directly subsequent and missing scheduled points.
- Current medical conditions – medical conditions ongoing at first dosing.
- Prior therapy: Any medication or therapy taken prior to start of first IMP dosing.
- Concomitant therapy: A medication or therapy ongoing at start of first IMP dosing, or starting after the first IMP dosing.
- Treatment emergent adverse event (TEAE): Adverse event with an onset (or worsening) on or after the time of the first IMP dosing.
- Time to achievement of PASI 50 (75): Day of first visit were PASI 50 (75) is observed.
- Analysis centers: Pooled small centers for analyses, as described in section 3.5.4.

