3.4.6.2 Statistical analyses

Primary efficacy endpoints

The co-primary endpoint response in PASI 75 at Week 12 (Day 84) is defined as 75% improvement in PASI score compared to baseline (i.e. percent of change from baseline $\leq 75\%$). The co-primary endpoint improvement in PGA at Week 12 (Day 84) is defined as reduction by 1 or more points on the PGA scale in comparison to baseline.

The comparisons of the treatment groups MP1032 300 mg bid and MP1032 150 mg bid, each vs. the placebo treatment, with respect to each, the PASI 75 rate and PGA improvement rate, at Week 12 (Day 84) will be evaluated by the CMH test stratified by (pooled) analysis center. The common odds-ratio with 95% confidence interval will be provided. The homogeneity of the individual odds-ratios will be assessed by the Breslow-Day test.

Secondary efficacy endpoints

Secondary efficacy endpoints will be evaluated descriptively. The methodology outlined at the top of this section 3.4.6.2 will be applied for pairwise treatment comparisons vs. placebo:

The PASI 50 responder rate at Week 12 (Day 84) will be evaluated according to the primary efficacy endpoints, as well as the PASI 75, PASI 50 and PGA improvement at Week 4 (Day 28) and Week 8 (Day 56) of the treatment phase and at follow-up, 4 weeks after end of treatment.

The change in the PASI score from baseline to each post baseline visit, respectively, will be evaluated using an analysis of covariance (ANCOVA) model, with treatment group and (pooled) analysis center as factors and baseline outcome as covariate, in both analysis sets, FAS and VCS.

The time to achievement of PASI 50 and PASI 75, respectively, will be evaluated using the Kaplan-Meier method. The study day of first achievement of PASI 50 and PASI 75, respectively, will be the considered event, with study day of last assessment as the time point of censoring, in case of no occurrences of PASI 50 or PASI 75. Pairwise treatment group differences will be tested by the log-rank test.

Location shift in change from baseline in PGA will be assessed using Hodges-Lehmann Estimation with comparison by the Wilcoxon rank sum test, in both analysis sets, FAS and VCS.

Descriptive summaries will be provided for each parameter by treatment group and by visit, if applicable. Percentages will be provided based on the number of non-missing cases, if not otherwise stated. For PASI and PGA the descriptive summaries will be performed in both analysis sets, FAS and VCS.

Subgroup analyses

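### The responder shells are titled LOCF although the SAP and protocol count missing PASI/PGA as failure, and the visit-assignment step before that rule has no Week 12 window

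*SAP*

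**What the plan says.** **Missing data.** For the success rates of the primary variables, SAP 3.5.1 states that "missing PGA assessments and/or any parts of the PASI assessments will be evaluated as failure to achieve improvement". Protocol 6.6 (version 2.0) has the same rule. Both then apply LOCF to descriptive analyses of PASI, PGA and BSA up to Day 84, and neither allows follow-up values to be imputed. SAP 3.4.6.2 extends the primary method: "The PASI 50 responder rate at Week 12 (Day 84) will be evaluated according to the primary efficacy endpoints". SAP 3.1 defines LOCF as "The last observed value (either scheduled or unscheduled) carried forward and used for all directly subsequent and missing scheduled points".

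**Shells.** In the SAP appendix, Tables 14.3.3 and 14.3.9 (PASI 75), 14.3.4 (PASI 50), and 14.3.15 and 14.3.18 (PGA improvement) all have LOCF in the title. Tables 14.3.3 and 14.3.15 hold the co-primary FAS results: CMH p-value, odds ratio and Breslow-Day test. The table list has no other responder table. SAP 1.3 reports no change from the protocol's statistical section.

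**Withdrawals.** Protocol 5.5.1 says "The observations and procedures scheduled for Visit 5 (End of Treatment) should be performed at the Early Termination Visit", so PASI and PGA will usually exist at withdrawal. SAP 3.5.3 then says "efficacy assessments performed at the time point of withdrawal, will be assigned to a planned visit as described in section 3.5.2". Under SAP 3.5.2 an off-schedule assessment is "assigned to the nearest, directly preceding or following planned visit, if that visit is missing". The tie rule reads: "If both planned visits are missing and the distances are equal, the assignment is performed to the following one". The section closes by keeping every other off-schedule assessment out of the evaluation and in the listings only.

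**Day 84 range.** The protocol flow chart allows +5 days and SAP Table 2 allows ±5 days. A footnote to Table 14.1.3 uses Days 80 to 91, together with at least 80% of planned exposure.

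**The concern.** A programmer who follows the shell titles carries values forward into the Week 12 responder status. One who follows SAP 3.5.1 counts the same patients as failures. Both can claim to have followed the SAP, and the two give different co-primary rates. Because SAP 1.3 declares no modification, the LOCF titles cannot be taken as a documented change of method.

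The visit-assignment step adds a second uncertainty. It decides whether a late withdrawer has a Week 12 value at all, before the failure rule is reached. Nothing ties it to the Day 84 visit window, and its wording can be read in two ways. The FAS is the primary efficacy set, so exclusions from the per-protocol set do not settle the matter.

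**Working it through.** **1. The plan's own figure.** SAP 2.2 gives 40 per group, 0.674 vs 0.400, two-sided alpha 0.10 and 80% power. With the pooled-variance chi-square formula and mean rate 0.537:

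n = [1.645 × √(2 × 0.537 × 0.463) + 0.842 × √(0.674 × 0.326 + 0.4 × 0.6)]² / 0.274² = 39.9, rounded up to 40; power at 40 is 0.801.

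The figure reproduces and is not in dispute. Its rates are used below.

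**2. Where the LOCF title can matter.**
- Week 16: SAP 3.5.1 forbids imputing follow-up, yet Table 14.3.3 shows Week 16 under the same title. The label cannot be literal there.
- VCS tables (14.3.9, 14.3.18): the set requires patients "who completed the visit 5 (Day 84) assessments of PASI and PGA". Apart from any retained discontinuations for related adverse events, there is little to impute at Week 12.
- FAS tables at Week 12: here the title and SAP 3.5.1 give opposite instructions.

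**3. Visit assignment, with Day 56 attended and Day 84 missed.**

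| Withdrawal day | Days from Day 56 | Days to Day 84 | Strict reading | Loose reading |
|---|---|---|---|---|
| 57 | 1 | 27 | listed only | Day 84 |
| 69 | 13 | 15 | listed only | Day 84 |
| 70 | 14 | 14 | listed only | Day 84 |
| 71 | 15 | 13 | Day 84 | Day 84 |
| 83 | 27 | 1 | Day 84 | Day 84 |

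Strict means the nearest planned visit must itself be missing. Loose means the nearest visit among those that are missing. On either reading, Days 71 to 83 become observed Week 12 values, up to 13 days early. On the strict reading, Days 57 to 70 fall under the closing sentence of 3.5.2 and are only listed. That conflicts with the SAP 3.1 LOCF definition, which carries unscheduled values forward.

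**4. Size.** The documents give no dropout rate or timing. Assumptions:
- 50 per arm in the FAS, with 10 withdrawals per arm (the plan recruits 150 for 120 evaluable, which is not a stated dropout rate);
- withdrawals spread evenly over Days 1 to 83, all assessed;
- response at 0.674 and 0.400 for completers and withdrawers alike.

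| Handling | Calculation | Difference |
|---|---|---|
| Missing = failure | 0.674 × 0.8 − 0.4 × 0.8 = 0.539 − 0.320 | 0.219 |
| Days 71–83 assigned to Week 12 | 13/83 × 10 = 1.57 patients per arm; + 1.57/50 × 0.274 = + 0.009 | 0.228 |
| Days 57–83 assigned (loose reading) | 27/83 × 10 = 3.25 patients per arm; + 3.25/50 × 0.274 = + 0.018 | 0.237 |
| LOCF for all 10 per arm | + 10/50 × 0.274 = + 0.055 | 0.274 |
| LOCF, withdrawers respond at half those rates | + 0.027 | 0.247 |

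Standard error of the difference under missing = failure: √(0.539 × 0.461/50 + 0.320 × 0.680/50) = 0.097. Power at two-sided 0.10 with 50 per arm is 0.72 under missing = failure and 0.87 under full LOCF.

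The direction is not fixed. Suppose carried-forward values exist for 10 active and 5 placebo withdrawers, all responding at 0.674. The difference is (26.96 + 6.74)/50 − (16 + 3.37)/50 = 0.287. With 5 and 10 it is (26.96 + 3.37)/50 − (16 + 6.74)/50 = 0.152.

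**The case against.** The strongest reply is that the SAP body governs. It names the success rates, gives the failure rule and confines LOCF to descriptive work. The shell titles look like a label applied loosely, as the Week 16 rows show. The trial is exploratory, p-values are descriptive, and counting an observed Day 78 score as Week 12 is a defensible choice.

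Much of this stands. The text of 3.5.1 is clear, the VCS tables are hardly affected, and restricting early-termination values to a window is partly preference. Table 14.1.3 is a disposition table that also uses exposure, so classing a patient there as discontinued does not contradict using the observed score.

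It does not dispose of the point. The label is not automatic, because the time-to-PASI shells (14.3.5, 14.3.6) omit it. Nor does the word descriptive separate the two methods cleanly, because SAP 3.4.6.1 says the data as a whole are evaluated descriptively. As listed, the only tables that will show the co-primary results carry a method that the text excludes for them.

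**Conclusion.** The contradiction between the failure rule and the LOCF shell titles is real, and in practice it concerns the FAS results at Week 12. The missing Week 12 window and the two readings of SAP 3.5.2 are a separate, smaller gap. Overall the point is minor.

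Under the stated assumptions the difference is 0.219 with missing = failure and at most 0.274 with LOCF, against a standard error of 0.097. The 0.274 is an upper bound for equal withdrawals with every value carried forward at full response. Visit assignment alone adds about 0.009 (0.018 on the loose reading). Unequal withdrawal can move the LOCF result either way.

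Three stronger readings are tempting, but the documents do not support them:
- A reader might infer three conflicting rules. SAP 3.5.2 and 3.5.3 are a prior step that settles whether a Week 12 value exists; 3.5.1 then applies if it does not. For Days 71 to 83 with an assessment, assignment and LOCF give the same value.
- A reader might infer that Day 70 is left unresolved. On the strict reading the closing sentence of 3.5.2 makes it listed only, and on the loose reading it goes to Day 84. What is open is which reading applies.
- A reader might infer that LOCF takes every withdrawal value to Week 12. That follows from SAP 3.1 alone, but the closing sentence of 3.5.2 excludes some of those values.

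**What to change.** Before unblinding:

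1. Remove LOCF from the titles of Tables 14.3.3, 14.3.4, 14.3.9, 14.3.15 and 14.3.18 and state there that missing counts as failure. If a LOCF responder table is wanted, add it as a labelled sensitivity analysis.
2. In SAP 3.5.1 to 3.5.3, state the order (assign visits first, then apply missing = failure) and say which reading of 3.5.2 applies. Say whether an early-termination value may count as Week 12 and within what window. Align the LOCF definition in SAP 3.1 with the listed-only sentence.
3. Reconcile the Day 84 range across the protocol flow chart, SAP Table 2 and the Table 14.1.3 footnotes, and make sure that completers seen outside it do not become failures by default.

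The cost is five titles, a few SAP sentences, one set of footnotes and one flow-chart entry. If early-termination values were limited to a window, the extra failures compared with the current assignment would be small under the same assumptions:
- Days 79–89: 8/83 × 10, about 1.0 per arm;
- Days 80–91: 9/83 × 10, about 1.1 per arm;
- Days 84–89: 13/83 × 10, about 1.6 per arm. Here completers seen on Days 79 to 83, who are on time under SAP Table 2, would also be affected unless a separate completer rule covers them.
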